3.8 Functional Image Processing and Statistical Analysis

3.8.1 Resting-state fMRI Data Processing

All functional imaging data were processed and analyzed using MATLAB R2022b (MathWorks) with the SPM12 toolkit, RESTplus v1.25, and DPABI v7.0 software packages. The preprocessing steps included: ①data format conversion; ②removal of the first 10 time points to eliminate unstable initial signals; ③head motion realignment and slice-timing correction. Individuals with head movements exceeding 2 mm or 2 degrees were removed; ④spatial normalization to the Montreal Neurological Institute template using the DARTEL registration algorithm, followed by resampling to an isotropic voxel size of $3\text{ mm} \times 3\text{ mm} \times 3\text{ mm}$; ⑤spatial smoothing using a 6-mm Gaussian kernel; ⑥linear detrending; ⑦regression of nuisance covariates, including 24-head motion parameters, white-matter signal, and cerebrospinal fluid signal; ⑧application of a 0.01 to 0.08 Hz bandpass filter.

Mean Regional Homogeneity (mReHo): ReHo maps were generated by calculating

Kendall's coefficient of concordance (KCC) using RESTplus V1.25 software. To minimize individual differences, the ReHo value of each voxel was normalized by dividing it by the global mean ReHo value of the entire brain, resulting in mReHo.

Mean Amplitude of Low-Frequency Fluctuation (mALFF) and its derived metric, mean fractional ALFF (mfALFF): The time series of each voxel was transformed into the frequency domain using a Fast Fourier Transform (FFT) to obtain the power spectrum. ALFF was calculated as the square root of the power spectrum. fALFF was defined as the ratio of the ALFF value in the low-frequency range (0.01–0.08 Hz) to the ALFF value across the entire frequency range (0–0.25 Hz). To minimize individual variability, the fALFF value of each voxel was normalized by dividing it by the global mean fALFF value of the whole brain, resulting in the mfALFF.

Functional images were transformed into a mirrored space after preprocessing. The mean BOLD time series for each voxel was extracted. Pearson's correlation coefficients were computed for mirrored voxels from the bilateral hemispheres to produce VMHC maps. The Fisher-z transform was used to enable subsequent group-level comparisons.

Z-score normalized Functional Connectivity (zFC) values: Brain regions exhibiting significant between-group differences in functional metrics were defined as regions of interest (ROIs). Functional connectivity between each ROI and the entire brain was computed using the RESTplus software. The resulting correlation coefficients were subsequently standardized using Fisher's r-to-z transformation to obtain zFC values.

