3.6.3 Imaging Examination

All participants underwent magnetic resonance imaging on the same day as the auricular acupuncture treatment using a Siemens Skyra 3T scanner equipped with a 16-channel head coil. The imaging protocols included conventional T1-weighted imaging (T1WI), T2-weighted imaging (T2WI), T2-fluid-attenuated inversion recovery (T2-FLAIR), high-resolution 3D-T1WI, and resting-state functional MRI (rs-fMRI). Prior to scanning, the participants were fitted with noise-canceling headphones and placed in a supine position. Head motion was minimized using foam padding. Participants were instructed to keep their eyes closed, maintain a wakeful state, and avoid engaging in any specific cognitive tasks. High-resolution T1-weighted structural scanning parameters were as follows: TR = 2300 ms, TE = 2.98 ms, FA = 9 degrees, FOV = 256 mm × 256 mm, voxel size = 1 mm × 1 mm × 1 mm, slice number = 176, thickness = 1 mm; for rs-fMRI, TR = 2160 ms, TE = 30 ms, FA = 90 degrees, FOV = 256 mm × 256 mm, matrix = 64 × 64, number of excitations (NEX) = 1, voxel size = 4 mm × 4 mm × 3 mm, thickness = 3 mm, slice gap = 0.75 mm, 40 slices, total

acquisition time = 518 s.

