3.7 Observational Indicators

Resting-state functional magnetic resonance imaging was used to conduct pre- and post-intervention comparative analyses in participants receiving auricular acupuncture.

Data collection is divided into two stages:

Baseline: Collection of demographic data, baseline fMRI scan, and clinical assessment (T0).

post-intervention:fMRI scan and clinical assessment immediately after the intervention (T1).

Primary Outcome Measure

Functional connectivity strength between the insula and the medial prefrontal cortex (MPFC)(T1-T0)

This connectivity strength serves as a proxy for the efficiency of information exchange between the “interoceptive hub” and “the self-referential/emotion-regulatory hub”. An increase following auricular acupuncture may reflect enhanced psychosomatic integration and top-down emotional regulation, suggesting a functional optimization of this circuit. Conversely, a decrease could indicate a disruption of pathological hyper-connectivity related to emotional constraint or an upregulation of control—mechanisms consistent with the observed alleviation of emotional symptoms

Secondary Outcome Measures

①Local brain activity indicators:regional homogeneity (ReHo), amplitude of low-frequency fluctuation (ALFF), fractional ALFF (fALFF)(T1-T0);

ReHo captures the temporal synchrony of neural activity within local brain regions. Following auricular acupuncture, increased ReHo in regions such as the insula and prefrontal cortex may reflect improved neural coordination and functional integration. Conversely, decreased ReHo in specific areas could indicate a modulatory effect on abnormally elevated local synchrony.

ALFF reflects the intensity of spontaneous neural activity in the brain. An increase in ALFF within emotion- and cognition-related regions following auricular acupuncture may indicate an elevation in baseline neural activity or metabolic activity in these areas. Conversely, a decrease in ALFF in regions such as the limbic system could reflect an

inhibitory modulatory effect of the intervention on hyperactivity, potentially contributing to emotional stabilization.

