fALFF: Changes in fALFF following the intervention allow a more specific assessment of auricular acupuncture's regulatory effects on intrinsic neural oscillations related to cognition and emotion. When interpreted in conjunction with ALFF changes, the direction of fALFF alteration can help elucidate the specific mechanisms through which auricular acupuncture modulates neural activity patterns.

②Interhemispheric coordination index: voxel-mirrored homotopic connectivity (VMHC)

The VMHC value quantifies the functional coordination between homotopic regions across the two cerebral hemispheres. Following auricular acupuncture, enhanced VMHC in regions associated with emotional regulation and cognitive control, such as the prefrontal cortex and anterior cingulate cortex, may suggest improved interhemispheric balance and integration of emotional processing. Conversely, changes in VMHC within specific regions could help clarify how the intervention modulates functional imbalances between hemispheres, particularly those related to constrained emotional states.

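### Section 3.8.1 band-passes the data to 0.01–0.08 Hz and then defines fALFF against the full band, so the denominator loses most or all of its out-of-band signal; it also smooths before ReHo

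*Combined protocol and SAP*

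**What the plan says.** Section 3.8.1 opens with a sentence on software, "All functional imaging data were processed and analyzed using MATLAB R2022b", and then lists eight preprocessing steps. Step 5 is Gaussian smoothing at 6 mm, step 7 is nuisance regression, and step 8, the last, is a band-pass at 0.01–0.08 Hz. No metric is given a separate branch.

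The metric definitions follow. fALFF is the "ratio of the ALFF value in the low-frequency range (0.01–0.08 Hz) to the ALFF value across the entire frequency range (0–0.25 Hz", and each voxel is then divided by the whole-brain mean to give mfALFF. ReHo is Kendall's coefficient of concordance, divided by its global mean. Neither paragraph says which step supplies its input. Only the VMHC paragraph does: "Functional images were transformed into a mirrored space after preprocessing".

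Section 3.7 lists these metrics as secondary outcomes, "regional homogeneity (ReHo), amplitude of low-frequency fluctuation (ALFF), fractional ALFF (fALFF)(T1-T0"), and gives fALFF an interpretive role: "When interpreted in conjunction with ALFF changes, the direction of fALFF alteration can help elucidate the specific mechanisms".

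**The concern.** The fALFF denominator needs the amplitude outside 0.01–0.08 Hz, which is what step 8 is there to remove. The list and the definition cannot both apply to the same time series, and nothing in the text assigns fALFF a different one.

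Section 3.7 reads mechanism from the direction of change in fALFF. A constant has no direction. If the filter is gradual rather than ideal, fALFF still varies, but a real change in low-frequency share is attenuated, and a null result could reflect the processing rather than the intervention.

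For ReHo the issue is milder. The statistic measures agreement between neighbouring voxels, and smoothing first imposes part of that agreement. The same kernel acts on both arms and both scans, so the cost is local specificity, not between-group bias.

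**Working it through.** The plan states no figure for this point, so there is none to reproduce. The inputs are the sequence in 3.6.3 ("for rs-fMRI, TR = 2160 ms, TE = 30 ms, FA = 90 degrees"; acquisition time 518 s), the 10 discarded volumes and the two frequency bands in 3.8.1, and 16 subjects per arm from 3.3.

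**Frequency content**
- Volumes: 518 / 2.16 = 239.8, taken as 240; 240 − 10 = 230.
- Frequency step: 1 / (230 × 2.16) = 0.00201 Hz.
- Highest frequency: 1 / (2 × 2.16) = 0.2315 Hz. The stated upper limit of 0.25 Hz cannot be reached at this TR.
- Non-zero bins: 230 / 2 = 115. Bins 5 to 39 fall in 0.01–0.08 Hz, which is 35. So (115 − 35) / 115 = 80 / 115, about 70% of the denominator's bins, lie outside the pass-band.

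**Ideal filter.** All 80 outside bins are set to zero, so denominator equals numerator and fALFF = 1 with SD 0. mfALFF is then 1 in every voxel, at both scans and in both arms. This needs no assumption about the spectrum.

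**Butterworth filter (simulated).** 3.8.1 does not state the filter type, so the spectrum and filter here are assumed. The base case is 1/f signal (exponent 1) plus white noise, with the signal share uniform on 0–1, and 4,000 series.

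| Input to fALFF | Mean fALFF | Correlation with true low-frequency share |
|---|---|---|
| Unfiltered | 0.35 | 0.78 |
| Zero-phase, order 2 | 0.81 | 0.42 |
| Zero-phase, order 4 | 0.86 | 0.29 |
| Single-pass, order 2 | – | 0.59 |
| Single-pass, order 4 | – | 0.37 |

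Twelve spectra were tried: exponent 0.5, 1 or 1.5, or a band-limited signal, each with share uniform on 0.1–0.5, 0.2–0.8 or 0–1. The mean was 0.32–0.50 unfiltered and 0.69–0.89 after Butterworth. The correlation fell in all 48 combinations (12 spectra × 4 filters). The smallest loss was 0.96 to 0.94, for a band-limited signal with a single-pass second-order filter.

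**Power.** The T1−T0 change was simulated with baseline share uniform on 0.2–0.6 and a shift of 0.2 in one arm, using 40,000 subject pairs per spectrum. Over 4 spectra and 4 Butterworth variants, the standardised between-arm difference kept 0.12 to 0.68 of its unfiltered size. For a two-sample t-test at two-sided 0.05 with 16 per arm (30 degrees of freedom), the noncentrality is d × √(16/2):
- d = 1.02: 1.02 × 2.83 = 2.89, power 80%.
- d = 0.68 × 1.02 = 0.69: noncentrality 1.96, power 48%.
- d = 0.12 × 1.02 = 0.12: noncentrality 0.35, power 6%.

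**ReHo.** The acquired grid is "voxel size = 4 mm × 4 mm × 3 mm, thickness = 3 mm, slice gap = 0.75 mm", so slice centres are 3 + 0.75 = 3.75 mm apart. Independent noise on a 4 × 4 × 3.75 mm grid was resampled to 3 mm and smoothed at 6 mm, taken as full width at half maximum. Neighbourhood size and interpolation are assumed.
- 27 voxels, linear interpolation: Kendall's W 0.17 before and 0.43 after smoothing.
- 27 voxels, cubic interpolation: 0.10 before and 0.36 after.
- The unrounded ratios are 2.6 and 3.6; with 7 voxels they are 1.8 to 2.1.
- Leaving out the resampling step, W on independent 3 mm noise rises from 0.037 to 0.337, about ninefold. The resampled figures are nearer to the plan's chain.

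**The case against.** The strongest reply concerns how 3.8.1 is read. Its opening sentence names software and does not say that every metric takes the output of step 8. Only VMHC is placed after preprocessing, and a full-band denominator presupposes unfiltered input. A separate branch for fALFF may therefore have been used. That is possible, but the text does not say so, and a reader who follows the list will not obtain fALFF. What is established is a fault in the plan as written, not that the analysis was run that way.

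The size is also open to challenge. Filter, spectrum, kernel definition and neighbourhood are all assumed, and the power model uses single raw fALFF series, not smoothed mfALFF maps. Even unfiltered fALFF needs d = 1.02 for 80% power, so a null result with 16 per arm would be weak evidence anyway. All of this stands: the simulated figures illustrate the harm and do not estimate it. The ideal-filter result is not affected.

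On ReHo, the metric remains computable, division by the global mean would absorb a uniform inflation, and smoothing the map afterwards keeps some blurring. That also stands, which is why only lost specificity is claimed.

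Finally, 3.8.1 takes its connectivity seeds from regions that differ between groups on the functional metrics. Corrected fALFF or ReHo maps could therefore change those seeds, although the definition of the primary outcome in 3.7 does not change.

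**Conclusion.** The concern holds. As written, the preprocessing list and the fALFF definition are incompatible. With an ideal filter the outcome is constant, whatever the data. With a Butterworth filter it varies but carries less information: under the assumed spectra, power for a shift that unfiltered fALFF would detect 80% of the time falls to between 6% and 48%. The loss depends on a filter and spectrum the plan does not state, and in the mildest case it is small.

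The ReHo ordering is a secondary weakness. Part of the measured local concordance comes from the kernel, with no claim of bias between arms.

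This should be fixed. It affects named secondary outcomes and possibly the seed regions drawn from them. Confidence is medium, because the processing actually used may differ from the text.

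**What to change.** In 3.8.1, state the input to each metric:
- ALFF and fALFF: the output of step 7, before the band-pass.
- ReHo: band-passed data without step 5, with the mReHo map smoothed at 6 mm afterwards.
- VMHC and functional connectivity: the output of step 8, as now.

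In the same edit, change the upper limit of the fALFF band from 0.25 Hz to 0.2315 Hz. This is a wording correction with no numerical effect.

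If this was already the practice, these sentences are the whole fix. If not, recompute fALFF and ReHo from the stored scans and then check whether the seed regions for zFC change. The cost is a few sentences and, at most, reordered processing steps for two secondary maps. No new data are needed, and the definition of the primary outcome stays as it is.

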Resting-state functional magnetic resonance imaging (rs-fMRI) provides a key tool for investigating the modulation effects of Vagus Nerve Stimulation (VNS) on brain functional connectivity (FC) by measuring the blood-oxygen-level-dependent (BOLD) signal arising from spontaneous neural activity in the absence of tasks. Functional connectivity (FC), which refers to temporal correlations in spontaneous neural activity between distinct brain regions, is known to be aberrant in various neurological disorders [8-9]. Specific studies have demonstrated that aVNS can significantly modulate FC in multiple brain networks. Studies have indicated that aVNS attenuates negative FC between the insula and the medial prefrontal cortex (mPFC), a mechanism that may enhance the balance between interoceptive awareness and cognitive experience [1]. In patients with primary insomnia, rs-fMRI analyses revealed that taVNS reduced FC between the mPFC and dorsal anterior cingulate cortex (dACC, part of the salience network), as well as between the mPFC and occipital cortex. This reduction in FC was positively correlated with improvements in the Pittsburgh Sleep Quality Index (PSQI) scores, suggesting that taVNS may improve sleep by modulating interactions between the default mode network (DMN), salience network, and the visual cortex [8]. Furthermore, in migraine research, repeated taVNS treatment modulated resting-state FC (rsFC) between brainstem areas (e.g., NTS, RN), the limbic system (bilateral hippocampus), pain-processing regions (bilateral postcentral gyri, thalamus, and mPFC), and basal ganglia (putamen/caudate). Notably, changes in rsFC between the RN and putamen were significantly correlated with a reduction in monthly migraine days, underscoring the role of taVNS in pain modulation pathways [9]. Another study on primary insomnia found that taVNS reduced FC between the basal forebrain (BF) and the visual cortex (e.g., middle occipital gyrus, fusiform gyrus), sensorimotor cortex (supplementary motor area), and mPFC. Weakening of the connection between the basal forebrain and middle occipital gyrus was associated with improvements in the Insomnia Severity Index (ISI). More importantly, baseline FC within the basal-forebrain–visual circuit predicts therapeutic response to taVNS, supporting its potential

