3.3 Sample Size

The sample size estimation for functional MRI (fMRI) studies was based on Desmond's research findings. When analyzing fMRI data using a liberal threshold of 0.05, at least 12 subjects are required to achieve 80% or higher activation intensity at the single-voxel level [11]. This study randomly recruited 32 subjects, with 16 subjects per group, to systematically analyze changes in brain function before and after auricular acupuncture intervention, combined with its efficacy.

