3.8.2 Clinical Data

Datasets: Intent-to-Treat (ITT) and Per-Protocol (PP) analyses were used.

Normally distributed continuous data were described as mean \pm standard deviation, and inter-group comparisons for normally distributed variables used independent-samples t-tests. Non-normally distributed scale data will be described as medians and interquartile ranges, and the Mann–Whitney U non-parametric test will be used for statistical analysis. Categorical data were analyzed using the Chi-square test.

All statistical analyses were performed using SPSS or R software. Statistical significance was set at $P < 0.05$.

四、Ethics and Participant Protection

Before the study begins, the study protocol (including questionnaires and the informed consent form) will be submitted for review and approval to the Ethics Committee of Taizhou People's Hospital Affiliated to Nanjing Medical University (ethics number: LSKY 2025-175-01). Any amendments to the study protocol will be submitted to the Ethics Committee for approval and record-keeping. All participants will be fully informed about the study purpose, procedures, potential risks, and benefits, and will provide written informed consent.

五、References

- [2] de Oliveira Rodrigues DM, Menezes PR, Machado Ribeiro Silotto AE, et al. Efficacy and Safety of Auricular Acupuncture for Depression: A Randomized Clinical Trial [J]. *JAMA Netw Open.* 2023;6(11):e2345138.

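### The primary outcome, change in insula–mPFC connectivity, has no region definition or extraction step, and the only connectivity rule in the plan takes its seeds from between-arm differences

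*Combined protocol and SAP*

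**What the plan says.** Section 3.7 gives one primary outcome: "Functional connectivity strength between the insula and the medial prefrontal cortex (MPFC)(T1-T0"), where T0 is the baseline scan and T1 the scan immediately after the intervention.

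Section 3.8.1 describes preprocessing and then the maps for mReHo, mALFF, mfALFF and VMHC, all of which serve secondary outcomes. Its last paragraph is the only text on computing seed-based connectivity: "Brain regions exhibiting significant between-group differences in functional metrics were defined as regions of interest (ROIs"). It continues: "Functional connectivity between each ROI and the entire brain was computed using the RESTplus software", followed by Fisher's r-to-z transformation.

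Section 3.8.2, headed Clinical Data, lists the tests. For normally distributed variables, "inter-group comparisons for normally distributed variables used independent-samples t-tests"; Mann–Whitney and Chi-square tests cover the other cases. None is assigned to a named outcome.

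Two places describe the comparison as before versus after. Section 3.7 opens with "Resting-state functional magnetic resonance imaging was used to conduct pre- and post-intervention comparative analyses in participants receiving auricular acupuncture", and Section 3.3 states the purpose of the 16 subjects per group as "to systematically analyze changes in brain function before and after auricular acupuncture intervention, combined with its efficacy".

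**The concern.** A primary outcome has to be computable from the plan by someone who has not seen the results. Here the named quantity is a connection between two large regions, and the plan does not say which part of each, on which side, or how left and right are combined. The rule that is given leads elsewhere: it starts from whatever differs between the arms and ends in whole-brain maps.

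Two things are at stake. Two analysts who follow the text faithfully could report different primary results, or one of them none. And if the 3.8.1 rule supplies the primary value, the pair is reported only when one of its regions already differs between the arms in the same scans, so that reporting depends on the result.

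**Working it through.** The plan gives no figure for this outcome that could be reproduced: the sample size in 3.3 rests on single-voxel activation, with no effect size or SD for insula–mPFC connectivity. The check is mainly a reading of the text.

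**Step 1. What an analyst needs, and what the plan supplies.**

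| Needed | Supplied |
|---|---|
| Insula region (label or coordinates, side) | Not given |
| mPFC region (same) | Not given |
| Rule for combining sides | Not given |
| Extraction of the pair's value at T0 and T1 | Not given; 3.8.1 goes from seed to whole brain |
| Transformation | Fisher r-to-z (3.8.1) |
| Change score | T1 minus T0 (3.7) |
| Between-arm test | Generic independent-samples t-test (3.8.2), not linked to this outcome |

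The background cites a taVNS study of this same connection, but no section says that its regions are adopted.

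**Step 2. Follow the 3.8.1 rule as written.** In context, the functional metrics are probably the four just described (mReHo, mALFF, mfALFF, VMHC). The time point and the threshold are not stated.

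- Insula selected: there is a seed map, but the mPFC target within it is undefined.
- mPFC selected: the same, with the insula undefined.
- Neither selected: no insula–mPFC value is produced.

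**Step 3. Can the selection effect be sized?** For one fixed pair with no true difference, tested at 0.05:

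P(selected and connectivity test significant) ≤ P(connectivity test significant) = 0.05.

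So the trial-level error for that pair does not exceed 5%. Among trials in which the seed was selected, the rate depends on the correlation between the selecting metric and the connectivity change. The documents do not give it. A simulation under the null with 16 per arm and selection at P < 0.05 (200,000 trials per value) gives:

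| Assumed correlation | False positives among selected seeds |
|---|---|
| 0 | about 5% |
| 0.3 | about 9% |
| 0.5 | about 17% |
| 0.7 | about 32% |

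These are illustrations over an assumed range that includes no harm. They are not an estimate for this trial.

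**Step 4. What adjusting for T0 does.** Let r be the T0–T1 correlation and k the ratio of the T1 SD to the T0 SD, both assumed. Relative to the T0 variance:

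- variance of the change = 1 + k² − 2rk
- ANCOVA error variance = k²(1 − r²)
- ratio = k²(1 − r²) / (1 + k² − 2rk)

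With k = 1 this reduces to (1 + r)/2: 0.65, 0.75 and 0.85 at r = 0.3, 0.5 and 0.7.

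With unequal variances the range widens:

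- k = 0.8, r = 0.3: 0.64 × 0.91 / (1.64 − 0.48) = 0.5824 / 1.16 = 0.50
- k = 1.25, r = 0.7: 1.5625 × 0.51 / (2.5625 − 1.75) = 0.7969 / 0.8125 = 0.98

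With all 32 participants, error degrees of freedom fall from 32 − 2 = 30 to 32 − 3 = 29.

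**The case against.** **The 3.8.1 rule is only a follow-up of the secondary metrics.** This is plausible, since it comes straight after them. But then no rule is left for the primary outcome. Either reading leaves a gap.

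**The test is there.** A T1-minus-T0 change with an independent-samples t-test is the natural reading: 3.8.2 sits under a parent section on image processing and statistical analysis, and the outcomes that 3.7 names are all imaging measures. This largely stands. What remains is that the test is not linked to the outcome and the value to be tested is not defined.

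Three stronger readings are tempting, and the documents do not support them:

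- *A within-arm pre-post analysis is planned.* The wording in 3.3 and 3.7 could suggest it, but no paired test is listed, 3.8.2 speaks of comparisons between groups, the design is parallel-group and sham-controlled, and the SA arm is itself named sham auricular acupuncture. The wording needs aligning and no more.
- *Connectivity strength might be taken as an absolute value.* Fisher's z of a correlation keeps its sign, and no step removes it. Stating that the value is signed is a clarification.
- *Seed selection inflates the false-positive rate.* It may, among selected seeds, but the size is unknown and may be zero, and the trial-level error for one fixed pair does not exceed 5%.

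A last objection is that ANCOVA is a preference, because the t-test on the change is valid. It is valid. ANCOVA is proposed because it uses the T0 value already collected and generally reduces the error variance.

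**Conclusion.** The concern holds as a defect of definition. The sole primary outcome has no regions and no extraction step, and the one connectivity rule in the plan does not deliver it except when a between-arm difference has already put the insula or mPFC among the seeds. This goes beyond missing detail, because a stated rule leads away from the stated outcome. It should be settled before the primary analysis is run.

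Confidence is high for the missing regions and extraction. No size is claimed for selection bias, since the threshold and the correlation between metric and connectivity are not given. The gain from T0 adjustment rests on assumptions: an error variance of 65–85% of the change-score variance for r of 0.3–0.7 with equal T0 and T1 variances, or about 50–98% if the SD ratio lies between 0.8 and 1.25.

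**What to change.** In 3.8.1:

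1. Define the insula and mPFC regions by atlas labels or coordinates, with side and a rule for combining sides, before group maps or allocation are seen.
2. Compute one signed Fisher-z insula–mPFC value at T0 and one at T1 for every participant with usable scans, given the head-motion removals already in that section.
3. Make the AA-versus-SA comparison of the T1-minus-T0 change, adjusted for T0 by ANCOVA, the single primary test at two-sided 0.05. Keep the plan's t-test on the change as a sensitivity analysis.
4. Label the data-selected seed analysis exploratory, and state its metrics, time point, threshold and multiple-comparison correction.

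In 3.3 and 3.7, align the before-and-after wording with the between-arm comparison and call any within-arm result descriptive. In 3.8.2, link the test to the primary outcome by name. If group maps have already been seen, declare the change post hoc.

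The cost is wording, a short extraction script, one degree of freedom for the covariate, and less freedom in choosing which connection is reported. No new scans or participants are needed, and there is no material loss of power against the plan's own between-arm t-test.

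### If VMHC differences define seeds, zFC at a seed's mirror region nearly repeats the comparison that selected it and is not independent evidence

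*Combined protocol and SAP*

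**What the plan says.** Section 3.7 lists VMHC as a secondary outcome. Section 3.8.1 defines it: "Pearson's correlation coefficients were computed for mirrored voxels from the bilateral hemispheres to produce VMHC maps". It adds: "The Fisher-z transform was used to enable subsequent group-level comparisons".

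The next paragraph of 3.8.1 sets the seed rule: "Brain regions exhibiting significant between-group differences in functional metrics were defined as regions of interest (ROIs". The target of each seed is then given: "Functional connectivity between each ROI and the entire brain was computed using the RESTplus software". The scale matches that of VMHC: "The resulting correlation coefficients were subsequently standardized using Fisher's r-to-z transformation to obtain zFC values".

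The zFC paragraph ends there. It does not name the metrics that define seeds, the threshold for selection, the between-arm test on zFC, or any region left out of the search. It also does not say whether a seed taken from a VMHC map lies in one hemisphere or covers both mirrored clusters. The only significance level and between-arm test are in section 3.8.2, under Clinical Data: "Statistical significance was set at $P < 0.05" and "inter-group comparisons for normally distributed variables used independent-samples t-tests". Section 3.3 gives the size: "This study randomly recruited 32 subjects, with 16 subjects per group".

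**The concern.** VMHC at a voxel is its correlation with the mirror voxel. Take a one-hemisphere seed picked because that correlation changed differently in the two arms. The whole-brain zFC search for the seed includes the mirror region, where zFC is the correlation of the seed's mean signal with the mirror voxels. The participants, scans and scale are the same, and the pair of regions is nearly the same.

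The zFC test at that location therefore starts from a statistic already known to be large, but is judged against a reference distribution that ignores this. A chance VMHC difference would tend to return as a significant connectivity finding and be read as two metrics agreeing, when there is one observation. Functional connectivity is the trial's headline construct, and section 3.7 interprets VMHC as interhemispheric balance, so such agreement would be tempting to report. The size of the zFC difference there would also be overstated.

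**Working it through.** **Stated figure.** The plan gives no error rate for the zFC step beyond P<0.05, so there is nothing to reproduce. The 12-subject figure in section 3.3 carries no effect size or SD and does not bear on this point.

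**Inputs from the documents.** 16 per arm (3.3); level 0.05 and independent-samples t-test (3.8.2, assumed to carry over to the imaging maps; two-sided assumed), hence 16 + 16 − 2 = 30 degrees of freedom.

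**Assumptions.** No true difference between arms. ρ is the correlation, across participants, between the change in VMHC and the change in zFC at the mirror region. The selection level is a. The documents give neither ρ nor a, so both are varied.

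**Formula.** With Z1 the selecting (VMHC) statistic, Z2 the mirror-region zFC statistic and k the two-sided critical value for level a:

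P(|Z2|>1.96 given |Z1|>k) = 2[Φ₂(−k, −1.96; ρ) + Φ₂(−k, −1.96; −ρ)] / a

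Φ₂ is the bivariate normal distribution function. The same quantity was simulated with t-tests at 16 per arm (400,000 null trials per ρ).

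| ρ | a = 0.05: t-test simulation | a = 0.05: formula | a = 0.001: t-test simulation | a = 0.001: formula |
|---|---|---|---|---|
| 0.5 | 18% | 19% | 39% | 42% |
| 0.8 | 43% | 44% | 88% | 92% |
| 0.9 | 58% | 59% | 98% or more | above 99% |
| 0.95 | 70% | 71% | nearly 100% | nearly 100% |
| 0.99 | 86% | 87% | nearly 100% | nearly 100% |

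With ρ = 0 and a = 0.05, that is, a seed chosen independently of the test, the simulated rate is 4.9%.

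**Which ρ is plausible.** A time-series simulation used the plan's acquisition: 518 s / 2.16 s is about 239 volumes, less 10 dropped = 229, in the 0.01-0.08 Hz band. It took an assumed 10-voxel seed and the T1−T0 change. With selection at 0.05:
- weakly coherent seed voxels: ρ about 0.8, rejection 37-41%;
- moderate coherence: ρ about 0.93-0.945, rejection 62-71%;
- high coherence: ρ about 0.99 or more, rejection 88-93%.

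Each setting rests on only about 90-110 selected seeds, so these rates are rough.

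**Joint rate.** The chance that a given null region is both selected and significant at its mirror is a times the conditional rate. At a = 0.05 this is 0.05 × 0.43 = 2.2% to 0.05 × 0.86 = 4.3%. At a = 0.001 it cannot exceed 0.1%. The unconditional rate of the zFC test stays at 5%.

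**Effect size.** With 30 degrees of freedom, selection at P<0.05 needs |t| > 2.042, an observed VMHC difference of at least 2.042 × √(2/16) = 0.72 SD. The zFC difference expected at the mirror is about ρ times the VMHC difference. Even for a seed that only just passes, that is 0.8 × 0.72 = 0.58 to 0.99 × 0.72 = 0.71 SD, when the truth is zero.

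**The case against.** Five things can be said for the plan.

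1. The chain is partly inferred: 3.8.1 does not name VMHC as a seed-defining metric and stops before any zFC test. That stands as a condition on the point. But VMHC is a listed outcome, is prepared for group comparison and is defined immediately before the seed rule, and this is a two-arm sham-controlled trial.

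2. VMHC and zFC are not the same quantity. One pairs single voxels in a mirrored space; the other pairs a seed mean with voxels. This also stands: the second test nearly repeats the first, and ρ below 1 expresses that. If seed voxels shared no regional signal, ρ and the rate could fall below the range given (18% at ρ = 0.5), still above 5%.

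3. No false-positive rate above nominal follows for the zFC analysis as a whole. Correct. A reader might infer from the conditional rates that most zFC findings would be false, or that a stricter VMHC threshold makes matters worse overall. The documents do not support either. The rates apply only once a null seed has been selected; a stricter threshold raises the conditional rate but makes such seeds rarer.

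4. A reader might carry the argument over to seeds selected on ReHo, because local synchrony resembles connectivity within the seed. The documents define ReHo as Kendall concordance scaled by the whole-brain mean, a different statistic, and no calculation supports the extension. Nor was mirror-region circularity shown for ALFF or fALFF seeds.

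5. If a VMHC seed spans both hemispheres, its mirror lies inside the seed and the simulated geometry does not apply. That stands for the numbers, though the same exclusion covers the case.

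**Conclusion.** The point holds for seeds selected on VMHC, at the seed's mirror region, provided that VMHC is among the seed-defining metrics and zFC is compared between arms at P<0.05. A significant zFC result there cannot count as evidence separate from VMHC, and its size is biased upward.

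The conditional rejection rate under no effect is about 43-87% for ρ of 0.8-0.99 with selection at 0.05, and about 90% to nearly 100% with selection at 0.001, against a nominal 5%. These are ranges under assumed values, not properties of the plan. The harm is double counting and an inflated effect at one location for one class of seed. Naming a fixed insula-mPFC pair for the primary outcome would not remove it from the secondary analyses.

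**What to change.** In section 3.8.1, for VMHC-selected seeds only:
- exclude the seed and its mirror (homotopic) region from the between-group zFC search mask, whether the seed is unilateral or bilateral;
- report seed-to-mirror connectivity only through VMHC;
- state that this connection is not counted as a separate or confirmatory finding.

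If VMHC is not meant to define seeds, or zFC is not meant to be tested between arms, a sentence saying so would settle the point instead.

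The cost is one mask operation and two sentences, with no new data or participants. The excluded voxels drop out of the zFC tables, but the VMHC map already carries the seed-to-mirror information. For seeds near the midline the mask also removes some adjacent medial cortex, so any margin around it should be kept small. Seeds selected on other metrics need no mirror mask on these grounds.
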